### 7.2.2 Secondary Objectives

1. To evaluate the efficacy of the HART-HN regimen at the minimum number of safe fractions at 1-year as measured by locoregional control and overall survival
  - a. To estimate 1-year locoregional recurrence, patients will be followed for locoregional recurrence during the 12-month follow-up period with death as a competing risk using the methodology of Fine and Gray. Cumulative incidence curve will be plotted to describe dynamics of locoregional recurrence over time.
  - b. To estimate 1-year overall survival, the Kaplan-Meier methodology will be used.
2. To assess patient quality of life during and after the HART-HN regimen at the minimum number of safe fractions as measured by a battery of quality of life and functional metrics.
  - a. Quality of life changes will be determined by measuring the following quality of life/toxicity scores at the time points specified in the study calendar: CTCAE version 5.0 scores, composite FACT-HN scores, composite MDADI scores, opioid use, EAT-10 questionnaire scores, Functional Oral Intake (FOIS) scores and Dynamic Imaging Grade of Swallowing Toxicity (DIGEST) grading. QOL measures will be summarized by descriptive statistics; no inferential statistics or hypothesis testing will be performed. The proportion of missing responses will be reported on QOL and functional measures.
  - b. To determine changes in quality of life and toxicity scores, longitudinal plots of these scores will be used to determine whether these return to baseline or improve after treatment.

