## STUDY SCHEMA

## STUDY CALENDAR

Study Assessment	Screening	Pre-Intervention*	Intervention**					Follow-up (until 12-months post RT)***			
Procedures	Day -30 to Enrollment	Simulation & Evaluations	RT 1	RT 2-4	RT 5	RT 6-completion	Final Fraction of RT (+/- 48 hours)	2, 4, and 6 wk Post-RT Follow-Up (+/- 7 days)	3 mo Post-RT Follow-Up (+/- 14 days)	6 mo Post-RT Follow-Up (+/- 14 days)	9 and 12 mo Post-RT Follow-up (+/- 14 days)
Informed Consent	X										
Physical Exam (Radiation Oncologist) 	X		X (One visit no later than 24 hours after fraction 5)			X (One visit to be completed no later than 24 hours after final RT fraction)		X	X	X	X
Physical Exam (Surgical Oncologist) 	X								X	X	X
Performance Status	X		X (One visit no later than 24 hours after fraction 5)			X (One visit to be completed no later than 24 hours after final RT fraction)		X	X	X	X
Medical History	X										
Concomitant Medications	X		X (One visit no later than 24 hours after fraction 5)			X (One visit to be completed no later than 24 hours after final RT fraction)		X	X	X	X
AE Assessment	Recorded until completion of the 12-month follow-up period										
Basic Metabolic Panel 	X										
Magnesium (Mg) 	X										
Fasting glucose 	X										
Pregnancy Test 	X										
CT/MR Simulation		X									
Radiotherapy 			X	X	X	X	X				
Radiation Planning		X									
SLP Evaluation		X						X	X	X	X
VFSS Study 		X							X	X	
DIGEST Grade		X							X	X	
FACT- HN Survey		X					X	X	X	X	X
MDADI Survey		X					X	X	X	X	X

Study Assessment	Screening	Pre-Intervention*	Intervention**					Follow-up (until 12-months post RT)***			
Procedures	Day -30 to Enrollment	Simulation & Evaluations	RT 1	RT 2-4	RT 5	RT 6-completion	Final Fraction of RT (+/- 48 hours)	2, 4, and 6 wk Post-RT Follow-Up (+/- 7 days)	3 mo Post-RT Follow-Up (+/- 14 days)	6 mo Post-RT Follow-Up (+/- 14 days)	9 and 12 mo Post-RT Follow-up (+/- 14 days)
Total opioid intake		X					X	X	X	X	X
Visual analog pain scale		X					X	X	X	X	X
Neck CT or MRI and Chest CT or PET/CT of chest 	X								X		

\* Should be completed before starting radiation treatment

\*\* Scheduled as per institutional guidelines and study protocol

\*\*\* If a subject has disease progression/relapse or subject withdrawal, then they will be followed as per follow-up requirements.

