# 1 BACKGROUND

## 1.1 Introduction

Mucosal head and neck squamous cell carcinomas (HNSCCs), including tumors of the oral cavity, pharynx, and larynx, are the ninth leading cause of cancer-related mortality worldwide, with an estimated 65,000 cases and 13,000 deaths in the United States in 2019 alone. Two-thirds of cases present with advanced stage disease requiring multi-modality therapy. Upfront surgical resection remains a principal management strategy for HNSCCs. Because recurrence rates after resection are high in the setting of adverse pathologic features, adjuvant post-operative radiation is frequently given to improve outcomes.

Conventional post-operative radiation is a long and grueling treatment course: radiation is delivered five days per week for six weeks in 30 low-dose fractions. For HNSCC patients, this means that while recovering from major oral or pharyngeal surgery, they are forced to experience months of additional toxicities including diminished salivary flow, difficulty swallowing, and painful ulcerations of the mouth and throat (mucositis). Patients may find the prospect of undergoing a six-week course of radiation after surgery overwhelming and many refuse adjuvant therapy despite the very high risk of disease relapse. Even among patients who undergo post-operative radiation, excessive toxicities frequently cause breaks in therapy resulting in a prolonged treatment package time (time from surgery to completion of radiation), a feature associated with increased risk of both cancer recurrence and decreased survival. Even worse, such toxicities may prohibit completion of the full treatment course. ***Shortening the duration of therapy*** would increase the number of HNSCCs patients who receive the full course of indicated post-operative radiation on time and without interruption.

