### 1.3 Study Innovation

Several aspects of the HART-HN framework (**Figure 2**) for delivering post-operative radiation to patients with mucosal HNSCCs are innovative.

- a. Compressed Time Frame:** Unlike conventional post-operative radiation, which is delivered to a total dose of 60 Gy in 30 fractions over six weeks, HART-HN would be delivered to a total cumulative dose of 32.5-42 Gy in five to ten fractions over one to two weeks. Though the cumulative radiation dose for HART-HN is lower than for conventional post-operative radiation, we predict HART-HN to be at least as efficacious as conventional post-operative radiation for HNSCCs based on both empiric principles and analogous data from other malignancies. Accelerated repopulation of tumor cells after surgery and during radiotherapy is a principle mechanism of treatment failure in HNSCCs. From tumor line models, the estimated kickoff time for such repopulation is estimated at 21-35 days after initiation of therapy. As post-operative radiation is usually initiated as soon as three to four weeks after surgery, patients receiving HART-HN will complete surgery and radiation therapy within 30-45 days, before tumors begin to rapidly repopulate, thus reducing the risk of failure. Given the short treatment time-course we also anticipate that breaks in radiotherapy will be unlikely. Additionally, radiation regimens similar to HART-HN have long been used in post-operative treatment of resected melanomas with excellent LRC upwards of 90%.

**Figure 2.** Comparison of conventional post-operative radiation (PORT) and HART-HN. HART-HN reduces the overall treatment time compared to conventional therapy allowing patients to initiate and complete adjuvant radiation prior to developing acute effects of therapy and reducing overall treatment package time. Patients receiving HART-HN may have a shorter total duration of acute effects of therapy (yellow) and therefore tolerate it better than conventional therapy.

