Patients will undergo standard consultation to receive adjuvant head and neck radiotherapy for HNSCC and will be determined to be eligible for the clinical trial. If eligible, patients will receive informed consent about the risks and benefits of the trial and if they accept, will sign confirming their enrollment. Patients will then undergo standard radiotherapy simulation including CT simulation with and without IV contrast and/or MRI simulation with and without Gadolinium contrast. Patients will complete baseline FACT-HN and MDADI surveys. Patients will also be followed with a speech and language pathologist (SLP) and undergo videofluoroscopic swallow studies (VFSS) prior to treatment, 3 months after treatment and 6 months after treatment, as is standard of care in the treatment of HNSCCs and will be graded by the Dynamic Imaging Grade of Swallowing Toxicity (DIGEST) scale.

A radiation treatment plan will be developed as per the details in Section 5.1 with two target volumes: the PTV\_High (defined as the operative bed plus a 3 mm margin) will receive the experimental dose over the experimental number of fractions (BED3 of ~100, the BED3 of 60 Gy in 30 fractions) and the PTV\_Low (elective lymph node regions plus 3 mm setup margin) will receive a subclinical dose over the experimental number of fractions (BED3 of ~86.4, the BED3 of 54 Gy in 30 fractions).

Patients will then undergo daily image-guided radiotherapy on a Monday-Friday basis for the total number of experimental fractions. During treatment, all patients will be evaluated for acute toxicities at least once every five fractions with a physician visit. Additionally, patients will complete repeat FACT-HN and MDADI surveys on the day of treatment review.

After completion of the HART-HN, patients will be seen in follow-up at the following time points after completion of radiotherapy: bi-weekly for the first 6 weeks, at 3 months, 6 months, 9 months and 12 months. Patients will complete repeat FACT-HN and MDADI surveys to assess for quality of life outcomes at each follow-up. Repeat imaging including a PET/CT or Chest CT (with or without contrast) and a diagnostic CT (with or without contrast) or MRI of the neck will be ordered at the 3-month (+/- 2 weeks) follow-up timepoint. A head and neck CT or MRI may be ordered at any time, if clinically indicated.

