### Inclusion Criteria

1. Patients 18 years or older with gross totally resected (R0 resection) HPV-negative squamous cell carcinoma of the head and neck (squamous cell carcinoma of the larynx, hypopharynx, oropharynx, oral cavity, nasal cavity, paranasal sinuses or carcinoma of unknown head/neck primary) who have at least 1 of the following intermediate risk factors for adjuvant radiation:
  - a) **Pathologic Node Positive Disease**
  - b) **Perineural Invasion**
  - c) **Oral cavity cancer with depth of invasion of at least 5 mm**
  - d) **Lymphovascular Space Invasion**
  - e) **Pathologic T3 or T4 disease**
2. Zubrod performance status 0-2.
3. Patients must have the psychological ability and general health that permits completion of the study requirements and required follow up.
4. Inclusion of Covid-19 positive patients will be based on standard institutional protocol.
5. Female patients must meet one of the following:
  - Postmenopausal for at least one year before the screening visit, or
  - Surgically sterile (i.e. undergone a hysterectomy or bilateral oophorectomy), or
  - If subject is of childbearing potential (defined as not satisfying either of the above two criteria), agree to practice two acceptable methods of contraception (combination methods requires use of two of the following: diaphragm with spermicide, cervical cap with spermicide, contraceptive sponge, male or female condom, hormonal contraceptive) from the time of signing of the informed consent form through 90 days after the last dose of study agent, AND
    - Agree to practice true abstinence when this is in line with the preferred and usual lifestyle of the subject. (Periodic abstinence [e.g., calendar, ovulation, symptom-thermal, post ovulation methods] and withdrawal are not acceptable contraception methods).
6. Male patients, even if surgically sterilized (i.e., status post vasectomy), must agree to one of the following:
  - Practice effective barrier contraception during the entire study period and through 60 calendar days after the last dose of study agent, OR
  - Must also adhere to the guidelines of any study-specific pregnancy prevention program, if applicable, OR
    - Agree to practice true abstinence when this is in line with the preferred and usual lifestyle of the subject. (Periodic abstinence [e.g., calendar, ovulation, symptom-thermal, post ovulation methods] and withdrawal are not acceptable methods of contraception.)

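### Return to a post-operative, pre-radiation baseline cannot show that HART-HN left no lasting loss of quality of life or function

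*Combined protocol and SAP*

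**What the plan says.** Item 2a of Section 7.2.2 lists the scores: CTCAE, FACT-HN, MDADI, opioid use, EAT-10, FOIS and DIGEST. They are to be summarised descriptively, without testing. Item 2b then gives the one rule for interpreting them: "longitudinal plots of these scores will be used to determine whether these return to baseline or improve after treatment". No absolute level or clinically important difference is named.

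Where the baseline falls:

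- Inclusion criterion 1 requires "gross totally resected (R0 resection) HPV-negative squamous cell carcinoma of the head and neck", so every patient has already had surgery.
- The Study Calendar puts the first FACT-HN, MDADI, opioid, speech-language and swallow-study assessments in the pre-intervention column, with the note "Should be completed before starting radiation treatment". None is scheduled before surgery.
- Section 3.1 agrees. After consent and simulation, "Patients will complete baseline FACT-HN and MDADI surveys". Swallow studies are done "prior to treatment, 3 months after treatment and 6 months after treatment".
- Section 1.3 says that "post-operative radiation is usually initiated as soon as three to four weeks after surgery".
- Section 1.1, describing conventional treatment, says of patients that "while recovering from major oral or pharyngeal surgery, they are forced to experience months of additional toxicities".

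The eligibility criteria set no interval between surgery and baseline, and time since surgery does not enter the analysis. The trial has one arm. Section 2 leaves comparison with conventional radiation to later trials.

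**The concern.** A score that returns to baseline reads naturally as recovery from treatment. Here the baseline may itself be lowered by recent surgery. A patient who would have gone on improving without radiation, but whose improvement is cancelled by a lasting radiation effect, ends at the baseline value and meets the criterion.

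This matters because of what the primary endpoint leaves out. The toxicity limb of the DLT definition in Section 7.2.1 is set at Grade 4 or higher. Lasting but lesser problems with swallowing, diet or opioid use would have to show in the quality-of-life and function scores and in the CTCAE grades, and item 2b applies the same rule to all of these. A late finding of return to baseline would then go forward, without qualification, into the comparative trials this study is meant to support.

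**Working it through.** The plan gives no SD, effect size or margin for this analysis, so it has no figure to reproduce. The check covers timing, then what the change score measures, then an illustration.

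**1. Timing.** With radiation starting 3 to 4 weeks after surgery and lasting 1 to 2 weeks (Section 1.3), and the last visit about 52 weeks after radiation:

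- Baseline: before the first fraction, so at about 3 to 4 weeks after surgery on the usual early timing.
- Last visit: from 3 + 1 + 52 = 56 to 4 + 2 + 52 = 58 weeks after surgery.
- Start of radiation to last visit: from 1 + 52 = 53 to 2 + 52 = 54 weeks, during which surgical healing can continue.

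**2. What change from baseline measures.** Take a score for which higher is better, and let P be the level the patient would reach after full surgical recovery without radiation. Let S be the surgical recovery still to come at baseline, and R the lasting radiation loss.

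- Baseline = P − S
- Late score = P − R
- Change = (P − R) − (P − S) = S − R

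The plot shows S − R only. Separating the two would need a pre-surgical score, a comparator or an external recovery curve. The plan has none of these.

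**3. Illustration.** S and R are assumed, in SD units, with the SD of change assumed to be 1. The share of patients at or above baseline is Φ(S − R).

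| R | S | Mean change S − R | Share at or above baseline |
|---|---|---|---|
| 0.5 | 0 | −0.5 | 31% |
| 0.5 | 0.5 | 0.0 | 50% |
| 0.5 | 1.0 | +0.5 | 69% |
| 1.0 | 0 | −1.0 | 16% |
| 1.0 | 0.5 | −0.5 | 31% |
| 1.0 | 1.0 | 0.0 | 50% |

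For R = 0.5, and if all 18 patients were analysed, the expected numbers at or above baseline are 5.6, 9.0 and 12.4. The secondary objective concerns the selected fraction level, so the actual number will be smaller. S = R = 0 also gives a mean change of 0.0 and Φ(0) = 50%. On a change-from-baseline plot, no surgical recovery and no radiation loss therefore look the same as a full SD of each. Whenever S is at least R, the mean curve returns to or passes baseline despite the loss. Complete data would not alter this.

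**4. What depends on it.** The fraction decision in Section 7.2.1 uses the DLT rate against 33% up to 12 months. No quality-of-life baseline enters that rule.

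**The case against.** The case on the other side is substantial.

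- **The pre-radiation visit is the natural baseline for an adjuvant trial that enrols after resection.** This stands for acute effects. The inability to separate surgery from radiation comes from the single-arm design, and no choice of plot removes it.
- **Item 2a already summarises the listed scores at each time point, and plots show levels as well as change.** This stands, so part of the remedy is presentation. But item 2b's stated criterion is still return to baseline. Feeding-tube and tracheostomy dependence, recorded at each visit under Section 3.1, are missing from item 2a.
- **Item 2b attaches no formal conclusion, and nothing is tested.** This limits the weight of the point. It does not remove the need to say what a return to baseline can and cannot mean.
- **Absolute late status also mixes surgical and radiation deficits.** This stands, and the fix has to say so.

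Four stronger readings are tempting, and the documents do not support them:

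- A reader might infer that the regimen would pass as harmless overall. DLTs and adverse events are collected through 12 months independently of this baseline.
- A reader might place the baseline at the low point of surgical recovery. Sections 1.1 and 1.3 give timing and a general description, not function scores.
- A reader might conclude that the bias always favours the regimen. It needs surgical recovery still to come. If R exceeds S, scores stay below baseline, and recurrence would also lower them.
- A reader might think the opioid claim in Section 1.2 would be settled favourably. That claim compares HART-HN with conventional radiation, and a single-arm plot cannot answer it either way.

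**Conclusion.** The point holds for the descriptive secondary conclusion on quality of life, function and toxicity scores. Because the baseline is post-operative and there is no comparator, return to baseline or improvement over it is not evidence that HART-HN left no lasting deficit. If surgical recovery is incomplete at baseline, which the protocol's timing makes plausible but does not prove, the bias tends to favour the regimen. Its size cannot be computed, because the documents give no post-operative recovery curve; the SD figures show the mechanism only. Where radiation starts later than three to four weeks after surgery, less recovery may remain and the effect would be smaller. The DLT-based choice of fraction number is unaffected.

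**What to change.** Revise item 2b as follows:

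1. Use return to the pre-radiation baseline for acute effects only, from the end of radiation to 6 weeks.
2. At 3, 6 and 12 months, present absolute status beside change from baseline, as far as the calendar provides it: DIGEST at 3 and 6 months, FOIS, MDADI, FACT-HN and any opioid use. Add feeding-tube and tracheostomy dependence. Calendar footnote 7 links the FOIS score to the swallow study, so clarify whether FOIS is scored after 6 months.
3. Record the date of surgery and also plot scores by weeks since surgery.
4. State that return to, or improvement over, the post-operative baseline is not evidence of no lasting radiation effect, and that absolute late status reflects surgery and radiation together.

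The cost is a change of wording, one date from the chart and slightly more descriptive output. No new visit or instrument is needed. The late quality-of-life conclusion may come out less favourable.

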### 7.3 Sample Size Justification

The projected sample size will be 18, and we estimate an accrual rate of 3 patients every 2 months for a total estimated accrual time of 12 months. Patients will be recruited for the study based on whether they are unsuitable candidates for full course definitive chemoradiation either due to inability to tolerate cisplatin, locoregionally recurrent disease after surgery, or de novo metastatic disease. Based on our tumor board presentations, we typically have 6 patients who meet these criteria every month, so the proposed study of 18 patients can be easily accomplished within 12 months of opening if we are able to enroll 25% of eligible patients on this trial. We estimate an accrual of 3 study patients every 2 months (1.5 patients per month)

A review of patients treated at our institution with conventional post-operative radiotherapy from 2017-2019 had a one-year Grade 4+ toxicity rate of 9.5% with a one-year overall survival of 75%. As hypofractionated radiation has similar toxicity rates to conventional fractionation and non-inferior disease control in other malignancies, it is reasonable to expect that the HART-HN regimen may have a similar rate of late toxicity (9.5%) and at least similar survival outcomes to our patient population. In order to demonstrate the feasibility of detecting the correct MTD of the HART-HN regimen with a sample size of 18 patients, we performed Monte-Carlo simulation studies (1000 resamples each) with various *a priori* estimates of toxicity at the three doses (Table 1). For these simulations the following assumptions were made: (1) a constant hazard of observing DLT through the 12-month follow-up period; (2) a one-year survival of 75.4% (constant hazards as well); (3) a study accrual rate of three patients every two months; (4) toxicity as a function of dose level is modeled empirically; and (5) enrollment suspension prior to dose escalation as detailed at the end of section 7.1.

**Table. Results of Monte Carlo Simulation Studies Across Different Assumed Dose-Toxicity Profiles** (Bolded Numbers Reflect Values for the MTD Based on the Assumed Toxicity Profile)

Assumed 1-year toxicity rates at 42 Gy in 10 fractions, 38 Gy in 8 fractions and 32.5 Gy in 5 fractions	Probability that MTD is declared at 30, 32.5 or 35 Gy and the probability that the stopping rule is invoked
5%, 15%, 30%	15.9%, 28.2%, 55.9% , 0.0%
10%, 15%, 25%	24.4%, 25.2%, 50.3% , 0.1%
10%, 30% , 50%	51.0%, 27.8% , 21.1%, 0.1%
30% , 45%, 60%	86.0% , 6.2%, 1.1%, 6.7%

The probability of correctly identifying the MTD depends on the assumed toxicity at each dose level. However, using a wide variety of assumed toxicities at each dose level and a sample size of 18, results in a good probability of detecting the MTD for the majority of *a priori* estimates. Further, the chance of incorrectly selecting a dose level higher than the true MTD is reasonable (~20% or less at each assumed toxicity level).

No confidence intervals will be constructed due to the small sample size of our study.

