## 3 STUDY DESIGN

### 3.1 General Description

We propose a pilot Phase I study using a Time-to-Event Continuous Reassessment Methodology (TITE-CRM) design to estimate the minimum number of safe fractions. Patients with resected head and neck squamous cell carcinomas and no evidence of measurable disease with indications for adjuvant radiation alone and a life expectancy of at least 12 months will be enrolled. Patients with extracapsular extension and/or positive margins will be excluded due to data from multiple randomized trials suggesting a benefit for concurrent chemotherapy in this population. Baseline symptom evaluation will be obtained using validated surveys of head and neck cancer patients: the Functional Assessment of Cancer Therapy for the Head and Neck (FACT-HN) and the MD Anderson Dysphagia Inventory for Head and Neck (MDADI-HN). Patients will then undergo treatment using HART-HN and will subsequently be followed for up to 1 year.

Adjuvant radiation is the experimental therapy in this study, which will be the subject of fraction reduction while maintaining a BED3 of approximately 100 Gy. The minimum number of safe fractions will be determined as the radiation dose fractionation scheme with the least number of fractions at which there is no more than a 33% rate of dose-limiting toxicity (DLT) up to one year after treatment (to allow for the development of late toxicities from radiation).

All patients will receive a course of radiation therapy to the operative bed and regional elective using image-guided intensity modulated radiation therapy as detailed in section 5.1.

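### The accrual rate in section 7.3 rests on a count of a population that contradicts the eligibility criteria, so the 12-month accrual has no documented basis for this trial

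*Combined protocol and SAP*

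**What the plan says.** Section 7.3 (Sample Size Justification) gives the target and the pace: "The projected sample size will be 18, and we estimate an accrual rate of 3 patients every 2 months". From these it derives the duration, "for a total estimated accrual time of 12 months". It describes the people to be recruited as "unsuitable candidates for full course definitive chemoradiation either due to inability to tolerate cisplatin, locoregionally recurrent disease after surgery, or de novo metastatic disease". The pool is then counted on that description: "we typically have 6 patients who meet these criteria every month". The 12 months is said to be achievable "if we are able to enroll 25% of eligible patients on this trial". The same pace, three patients every two months, is assumption (3) of the Monte Carlo simulation in that section.

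The rest of the protocol describes other patients. The first inclusion criterion in section 4.6 asks for "Patients 18 years or older with gross totally resected (R0 resection) HPV-negative squamous cell carcinoma of the head and neck" with one or more listed intermediate-risk factors. Section 3.1 asks for "no evidence of measurable disease with indications for adjuvant radiation alone". The exclusion criteria remove extranodal extension, R1 or R2 resection, prior head and neck radiation and prior systemic therapy for the study cancer. The Protocol Summary and sections 2 and 7.1 also refer to resected, intermediate-risk disease.

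The timelines differ as well. Sections 7.1 and 7.3 give 12 months of recruitment, the Protocol Summary gives about two years to complete enrollment, and section 3.2 has the study complete about 24 months after opening.

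**The concern.** None of the three reasons for recruitment in section 7.3 is an inclusion criterion in section 4.6, and none of the intermediate-risk factors in section 4.6 appears in section 7.3. This is more than a stray sentence, because the next one counts the monthly pool on those reasons and then treats the people counted as eligible. The only empirical input to the accrual rate therefore describes a group that is not the trial population.

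Three things depend on that input: the claim that 18 patients can be enrolled in 12 months, the overall study timeline, and the accrual pace in the simulation. Under TITE-CRM the pace of accrual helps determine how much follow-up lies behind each dose assignment, so the reported selection probabilities are conditional on it. There is also a smaller practical cost: staff who took the sentence as a recruitment rule would screen patients whom section 4.6 turns away.

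**Working it through.** **Reproducing the plan's figure.** The inputs, all from section 7.3, are a pool of 6 a month, uptake of 25% and a target of 18.

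- Rate = pool × uptake = 6 × 0.25 = 1.5 a month, or 3 every two months.
- Time = target / rate = 18 / 1.5 = 12 months.

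The arithmetic is right. The question is what the 6 counts.

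**Comparing the two populations, reason by reason.**

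- Cisplatin intolerance: neither required nor excluded in section 4.6. Such a patient qualifies only if the resection, HPV and risk-factor criteria are also met.
- Locoregional recurrence after surgery: could qualify if re-resected to R0 with no prior head and neck radiation or systemic therapy. Otherwise it fails section 4.6.
- De novo metastatic disease: not excluded by name, but hard to square with no measurable disease, an R0 resection and an indication for adjuvant radiation alone.

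The overlap is thus neither nil nor known. In the other direction, a patient who meets section 4.6 and has none of the three features is not in the count at all. The error in the pool can run either way.

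**Range under assumed pools.** The documents give no monthly count of patients meeting section 4.6, so no corrected figure can be computed. The pools below are assumptions. Months = 18 / (pool × 0.25). Uptake needed to keep 12 months = 1.5 / pool.

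| Assumed eligible pool per month | Rate at 25% uptake | Months for 18 patients | Uptake needed for 12 months |
|---|---|---|---|
| 8 | 2.0 | 9 | 18.75% |
| 6 | 1.5 | 12 | 25% |
| 4 | 1.0 | 18 | 37.5% |
| 3 | 0.75 | 24 | 50% |

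**Pauses.** These times leave out the enrollment pause in section 7.1, which lasts until a DLT or for at least 3 months when three patients enroll rapidly at a new dose level. At 1.5 a month the average gap between patients is 1 / 1.5 = 0.67 month, so a full 3-month pause adds roughly 3 − 0.67 = 2.33 to 3 months. One pause gives 14.3 to 15 months, and three give 19 to 21. This is an approximation that assumes no DLT ends a pause early and ignores the lag between enrollment and the start of radiation. Because the pause is tied to rapid enrollment, it would add less if accrual were slower.

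**Timelines side by side.** Accrual of 12 months plus 12 months of follow-up is 24 months, which matches section 3.2 but leaves no time for treatment or pauses. Two years of enrollment, as in the Protocol Summary, implies 18 / 24 = 0.75 a month, or a pool of 0.75 / 0.25 = 3 a month at 25% uptake. Adding 12 months of follow-up gives 36 months, which does not match section 3.2.

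**The case against.** The strongest reply is that the defect leaves the scientific core untouched. Eligibility, the DLT definition, the 33% limit, the decision rule and the sample size of 18 do not depend on the sentence. Section 4.6 is a per-patient checklist with a signed confirmation, section 4.5 allows no waivers, and section 7.3 is not the recruitment procedure. Sections 4.2 and 7.4 also provide for reviewing accrual barriers and for closing the study if enrollment is unsatisfactory. All of this stands and limits the severity. It does not supply the missing count.

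Four stronger readings are tempting, and the documents do not support them.

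- A reader might infer that the count tells us nothing about eligible patients, or that accrual must be slower than planned. Some overlap is possible, and the eligible pool could exceed 6.
- A reader might infer that the simulation is invalid. Its accrual input is undocumented, but the documents do not show the direction or size of any effect on the selection probabilities. Slower accrual would give each TITE-CRM decision more follow-up.
- A reader might infer that ineligible patients will be enrolled. The signed eligibility check makes wasted screening the more likely cost.
- A reader might infer that the text was carried over from another study, since the simulation table's header also lists dose labels of 30, 32.5 and 35 Gy that are not this trial's regimens. The documents do not say so. Those labels need reconciling in their own right.

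**Conclusion.** The contradiction is real. Section 7.3 names and counts a recruitment population that conflicts with sections 3.1 and 4.6, so the 1.5 a month, the 12 months and simulation assumption (3) have no documented basis for this trial. The size of the error cannot be stated. At 25% uptake the illustrative range is 9 to 24 months for assumed pools of 8 down to 3 a month, before pauses, and only the pool of 6 reproduces the plan. The harm is mainly to feasibility and timeline, where the protocol already disagrees with itself (12 months against about two years). This should be fixed, but it does not undermine the design.

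**What to change.** 1. Delete the recruitment sentence in section 7.3, or rewrite it to match section 4.6.
2. Replace the pool of 6 with a tumor-board count of patients who meet section 4.6: R0 resection, HPV-negative, no extranodal extension, at least one listed risk factor, and no prior head and neck radiation or systemic therapy. State the period that the count covers.
3. Restate the accrual rate and duration from that count, with an allowance for the pauses in section 7.1.
4. Reconcile the Protocol Summary (about two years), section 3.2 (24 months to completion), and sections 7.1 and 7.3 (12 months).
5. If the rate changes, re-run the simulation at the new rate and report it as a sensitivity check beside the existing table.

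The cost is one chart or tumor-board count, a short simulation run, wording changes in several sections and possibly a longer stated accrual time.
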